2.8.4 Other safety data

2.8.4.1 ECG and cardiac imaging data

The following quantitative variables may be summarized if requested: ventricular rate, RR interval, PR interval, QRS duration, QT interval, and corrected QT interval (QTc). Fridericia (QTcF) correction will be presented for QTc.

Notable abnormal QTc will summarized by computing the number and percentage of subjects (including 95% confidence intervals for pooled DMC analysis) with:

- QTc > 500 msec
- QTc > 480 msec
- QTc > 450 msec
- QTc changes from baseline > 30 msec
- QTc changes from baseline > 60 msec
- PR > 250 msec

Summary statistics will be presented for ECG variables by visit and treatment group based on the entire study period. In addition, shift tables comparing baseline ECG interpretation (normal, abnormal, not available, total) with the worst on-treatment/study interpretation (normal, abnormal, not available, total) will be provided.

A listing of all newly occurring or worsening abnormalities (based on the treatment period/study period) will be provided, as well as a by-subject listing of all quantitative ECG parameters.

2.8.4.2 Vital signs

Analysis in vital sign measurement using descriptive summary statistics for the change from baseline for each post-baseline visit will be performed by vital sign and treatment group. Change from baseline will only be summarized for subjects with both baseline and post - baseline values and will be calculated as:

$$\text{change from baseline} = \text{post-baseline value} - \text{baseline value}$$

Vital signs will be summarized by visit based on the entire study period data. All vital signs will be listed with “on-treatment” flag displayed.

[figure not shown]
The number and percentage of subjects with newly occurring notable vital signs (within the treatment period) will be presented by treatment group. Subjects not meeting the following criteria at baseline but meeting at post-baseline are considered to be subjects with newly occurring abnormalities. Criteria for notable vital sign abnormalities are provided in Table 2-13 below:

[figure not shown]
Table 2-13 Criteria for notable vital signs in pediatric patients

Age group	Systolic BP(mmHg)	Diastolic BP(mmHg)	Pulse (bpm)
6 -11 yrs	90-130	50-80	50-105
12-17 yrs	90-145	55-90	45-95
18 yrs and over	90-139	60-89	60-100

If appropriate, data of subjects with newly occurring notable vital signs abnormalities will be listed in an additional listing.

Of note, systolic and diastolic blood pressure will be measured twice (measurements separated by 1 to 2 minutes), the average will be entered on the Vital Signs eCRF and will be used in the analysis.

2.8.4.4 Growth and Physical development

Body weight, height and BMI percentile will be summarized by treatment and visit.

Standard height, weight, and BMI curves will be obtained from the U.S. National Center of Health Statistics (www.cdc.gov/growthcharts) curves for ages up to 18 years. These growth curves will be used for all study subjects. The Center's files contain the L, M, and SD parameters needed to generate exact percentiles as follows:

$$z = \frac{\left(\frac{X}{M}\right)^L - 1}{L \times SD}$$

where X = physical measurement (e.g., patient's weight, height, and BMI)

M = median

SD = standard deviation

L = the power in the Box-Cox transformation

Percentiles for each patient at each time point will be calculated using the SAS function PROBNORM(z).

The number and percentages of subjects falling in low (i.e. <5), normal (i.e. 5-<95), or high (i.e. >= 95) growth percentiles will be summarized by treatment and visit. Shift from baseline in growth percentile categories, i.e., low (i.e. <5), normal (i.e. 5-<95), or high (i.e. >= 95), will be summarized by treatment and visit.

2.9 Pharmacokinetic endpoints

All completed subjects with quantifiable pharmacokinetic (PK) measurements of secukinumab will be included in the pharmacokinetic data analysis.

Serum concentrations will be expressed in mass per volume units. All concentrations below the limit of quantification (BLQ) as well as missing data will be labeled as such in the concentration data listings. BLQ concentrations will be included in the summaries. Serum concentration data from patients who missed a dose or doses will be excluded at the following visit(s).

PK concentrations will be summarized by eCRF visit and treatment. PK concentrations will also be presented by visit (i.e., CRF visit), dose group (75 mg, 150 mg, 300 mg) and body weight categories at visit (<25 kg, 25 to <50kg, \geq 50 kg). Per protocol, a subject will change into a higher or lower weight category and dose, when the subject's weight moves into a different weight category for two consecutive visits. This change is assessed from Week 12, then at week 16 and bimonthly until week 52 and at trimonthly visits in the extension phase. If such a change happens, in the PK summaries, at the concerned assessment points, the subject will be accounted in the new dose group (75 mg, 150 mg, 300 mg) and weight category group.

In addition to mean, standard deviation (SD), coefficient of variation (CV), median and quartiles, the geometric mean and geometric coefficient of variation (CV) and n(log) will be presented. The formula for deriving the geometric mean and CV (%) is as following:

- $CV\% = (SD/\text{mean}) * 100$,
- geometric mean = $\exp(\text{sum of log transformed data}) / \text{number of non-missing data points after log transformation}$,
- geometric CV = $\sqrt{\exp(\text{variance of log-transformed data}) - 1} * 100$.

In addition, sample number, concentration, sample date, elapse time since day of first secukinumab dose, reason excluding from analysis will be listed by treatment.

[figure not shown]
Values below lower limit of quantification/below detection limit will be imputed by 0.

Pharmacokinetic derived parameters AUC84-112d, Tmax and Cmax will be summarized by treatment group (AIN457 low dose and AIN457 high dose). Descriptive summary statistics include mean (arithmetic and geometric), SD, and CV (arithmetic and geometric), median, minimum and maximum. Derived pharmacokinetic parameters will be listed by treatment sequence.

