### **5.5.4 Instructions for prescribing and taking study treatment**

All study treatments will be administered subcutaneously throughout the study. All doses of study treatments at scheduled site visits will be administered at the study site after the study assessments for the visit have been completed. Prior to administration to the subject, the study treatment will be dispensed by the qualified site personnel appointed at the study site.

For home administrations the processes described earlier at [Section 5.5.2](#) must be followed.

The first study treatment administration will occur at the Randomization Visit (Day 1), after all study scheduled assessments have been performed (and inclusion/exclusion criteria confirmed) and only after the scheduled blood samples have been drawn. Similarly, at each other visit, all study assessments should be completed prior to the administration of study treatment.

Subjects will be administered study medication weekly for the first 4 weeks of the treatment period and then every 4 weeks until Week 204.

During the Follow-up period, no study medication will be administered.

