a Before randomizing the subject, the site must ensure that all assessments of the screening visit have been performed, all lab results are available and subject is eligible. Special attention must be given to tuberculosis testing as results take longer to be available.

 Apart from the Informed consent for this study signed by parent(s) /legal representatives, assent form will be completed as appropriate by the pediatric subjects.

 These assessments are supported by and are stored with the source documentation. However, data regarding to which inclusion/exclusion criteria are met are captured on the appropriate eCRF

 Information on Topical Corticosteroid medication, that a subject may use, is entered in the concomitant medications-topical corticosteroids eCRF

 Measured standing and barefoot, using the same stadiometer.

 Samples will be shipped to and analyzed by the central lab. At the discretion of the investigator, laboratory assessments need not to be performed again at Day 1-Randomization (R) visit if screening labs were performed within 7 days from randomization.

 If the first tuberculosis central lab test is indeterminate, the investigator may choose to perform a second test (as part of an unscheduled visit) or refer the subject for tuberculosis workup per local guidelines. If the result of any tuberculosis central lab test is "positive" or the results of two sequential tests are "indeterminate", the subject must be referred to have a tuberculosis workup per local guidelines (if no workup within 12 weeks prior to randomization is available). The subject will not be eligible for randomization if active tuberculosis is present or if latent tuberculosis is present and is untreated as per local guidelines.

 Urine pregnancy test will be performed locally. If there is a positive urine pregnancy test, study treatment must be withheld and a serum pregnancy test done at the same visit. Pregnancy tests will be performed in female subjects of child bearing potential, i.e. those who have started menstruation and/or are of age 12 or older.

 Samples shipped by the sites will be stored at the central laboratory and then shipped to reference laboratories for analysis. Each PK and IG blood sample should be collected pre-dose between Day 1 (Randomization) and Wk 52.

 CDLQI will no longer be completed once subjects reach 18 years of age

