cEOF assessments are to be conducted for subjects who complete treatment free follow up period and for subjects who discontinue this period early

dThe assessments performed at an unscheduled visit are at the investigator's discretion

Information on Topical Corticosteroid medication, that a subject may use, is entered in the concomitant medications- topical corticosteroids eCRF

Measured standing and barefoot, using the same calibrated stadiometer,

Samples will be shipped to and analyzed by the central lab.

If there is a positive urine pregnancy test, study treatment must be withheld and a serum pregnancy test must be done at the same visit and sent to central lab.

Pregnancy tests will be performed in female subjects of child bearing potential, that is those who have started menstruation and/or are of age 12 or older.

Samples shipped by the sites will be stored at the central laboratory and then shipped to reference laboratories for analysis. Each PK and IG sample should be collected pre-dose for Week 52 to Week 208.

An unscheduled IG and/or PK sample is collected only to replace an IG or PK sample not taken at a regular scheduled visit. In case unscheduled IG sample is taken, there should always be a matching unscheduled PK sample taken at the same time point.

CDLQI will no longer be completed once subjects reach 18 years of age

 For every visit, the weight measured at that visit will be entered into IRT

 Secukinumab will be dispensed at site visits. Between site visits, study medication will be administered every 4-weeks at home either by the subject (self-injection is allowed for subjects  $\geq$  12 years) or parent/caregiver until Week 204. In case subject or parent/caregiver does not feel confident in performing home administrations subjects will be allowed to continue to perform drug administrations at site. Home administrations in the years 2-4 occur at Wk 56, Wk 60, Wk 68, Wk 72, Wk 80, Wk 84, Wk 92, Wk 96, Wk 100, Wk 108, Wk 112, Wk 120, Wk 124, Wk 132, Wk 136, Wk 144, Wk 148, Wk 152, Wk 160, Wk 164, Wk 172, Wk 176, Wk 184, Wk 188, Wk 196, Wk 200, Wk 204. During the COVID-19 pandemic, or any other pandemic, study medication may be shipped to the patient's home and administration should be completed at the scheduled timepoints.

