## 14 Appendix 2: Blood collection log for pharmacokinetics and immunogenicity

**Table 14-1 Blood collection log for pharmacokinetics**

Visit	Timepoint	Volume	Analyte	Sample number 	PK collection number /Dose Reference ID 
Randomization/Day 1	Pre-dose	1 mL	AIN457 for PK	1	1
Week 4	Pre-dose	1 mL	AIN457 for PK	2	2
Week 12	Pre-dose	1 mL	AIN457 for PK	3	3
Week 13	168 hours 	1 mL	AIN457 for PK	4	3
Week 14	336 hours 	1 mL	AIN457 for PK	5	3
Week 15	504 hours 	1 mL	AIN457 for PK	6	3
Week 16	672 hours 	1 mL	AIN457 for PK	7	3
Week 24	Pre-dose	1 mL	AIN457 for PK	8	4
Week 52	Pre-dose	1 mL	AIN457 for PK	9	5
Week 104	Pre-dose	1 mL	AIN457 for PK	10	6
Week 156	Pre-dose	1 mL	AIN457 for PK	11	7
Week 208	672 hours 	1 mL	AIN457 for PK	12	8
Week 224	3360 hours 	1 mL	AIN457 for PK	13	8

 If a PK sample is collected at an unscheduled visit, the sample numbers will follow the pattern: 1001, 1002, etc.

 Scheduled time points for sample numbers 4, 5, 6, 7 (168, 336, 504 and 672 hours post-dose, respectively) refer to the last previous dose given at Week 12 (Dose Reference ID = 3)

 Scheduled time points for sample numbers 12 and 13 (672 and 3360 hours post-dose, respectively) refer to the last dose given at Week 204 (Dose Reference ID = 8)

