1.1 Study design

This is an open-label, parallel-group, two-arm, multi-center trial in pediatric subjects aged 6 years to less than 18 years with moderate to severe chronic plaque psoriasis.

Approximately 80 subjects (at least 60 patients with moderate severity) will be enrolled. It is expected that subjects will be enrolled in about 40 centers worldwide. It will be targeted to have at least 5 subjects in the < 25 kg weight, and at least 10 subjects in each of the other two weight groups (25 - <50 kg and \geq 50 kg). Subjects will receive the appropriate dose based on their body weight category. If a subject moves into a higher or lower weight group at two consecutive visits with weight measurements from Week 12 onwards, the subject will receive dosing according to the new (higher or lower) weight group respectively. The dose will be adapted starting from the visit of the second consecutive weight change.

The following study periods will be considered for analysis:

Screening Period

The screening period of up to 4 weeks will be used to assess eligibility of the subjects and to taper subjects off prohibited medication.

Treatment Period

The treatment period is defined as randomization to Week 208. In this period the endpoints are assessed and subjects are followed for long-term safety and efficacy. For safety analysis this is defined a last dose + 84 days exposure.

Follow-up Period

The treatment-free follow-up visits will be at Week 212, Week 216 and Week 224 (End Of Follow-up/EOF). Subjects who complete or discontinue treatment early are expected to perform the complete treatment-free follow-up period unless they start another systemic antipsoriatic treatment.

Of note: data from follow-up period for prematurely discontinued subjects will be included in the analysis of treatment period if appropriate.

Entire study period (Randomization to end of study (EOS)), including follow-up period (W212, W216 and W224 visits).

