2.2.1 Subgroup of interest

The primary endpoint(s), selected secondary [REDACTED] endpoints and selected safety endpoints will be evaluated using the subgroups defined in Table 2-1 where appropriate. Subgroup analyses for the study endpoints are represented in Table 2.2. [REDACTED]

Table 2-1 Subgroups definitions

Subgroup variables	Categories	Label for outputs	Suffix for outputs*
Randomization weight strata	body weight stratum (kg:<25, 25-<50, \geq 50)	Weight strata	a
Randomization disease severity strata	Disease severity strata (moderate, severe)	Disease severity strata	b
Age group	(<12 years or \geq 12 years)	Age group	c
Body weight and dose group*	AIN457 75 mg and <25 kg, AIN457 75 mg and 25-< 50 kg, AIN457 150 mg and \geq 50 kg; AIN457 150 mg and 25-< 50 kg, AIN457 300 mg and \geq 50 kg	Body weight by dose group	d

*In the final (Week 224) analysis, subjects will be accounted in their actual dose group and weight category group to evaluate doses adjusted to the body weight. Per protocol, a subject will change into a higher or lower weight category and dose, when the subject's weight moves into a different weight category for two consecutive visits. If such a change happens, starting from the next efficacy assessment after the dose change, the subject will be accounted in the new dose group (75 mg, 150 mg, 300 mg) and weight category group.

Table 2-2 Subgroup endpoints

Endpoint/analysis	Randomization strata including weight and disease severity	Age	Weight and by dose group
[REDACTED]			
Adverse event	X	X	X
PK concentration data			X
Demography and background characteristics	X	X	

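### SAP 2.9 does not define when a weight-driven dose change takes effect in the PK-by-dose tables; read plainly, it files a pre-dose sample from the old dose under the new one

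*SAP*

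**What the plan says.** SAP section 2.9, with the same text in the 2020 and 2023 versions, presents serum concentrations by visit, by dose (75, 150 or 300 mg) and by weight category at the visit. It gives the timetable for a change of weight group: "This change is assessed from Week 12, then at week 16 and bimonthly until week 52 and at trimonthly visits in the extension phase". The next sentence says that if a change happens, "at the concerned assessment points, the subject will be accounted in the new dose group (75 mg, 150 mg, 300 mg) and weight category group".

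Four other provisions fix when the new dose and the sample fall:

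- **Start of the new dose** (SAP 1.1, and Protocol 3.1): "The dose will be adapted starting from the visit of the second consecutive weight change".
- **Order of procedures** (Protocol 5.5.4): "at each other visit, all study assessments should be completed prior to the administration of study treatment".
- **Sample timing, Year 1** (Protocol Table 6-1, footnote 9): "Each PK and IG blood sample should be collected pre-dose between Day 1 (Randomization) and Wk 52".
- **Sample timing, Years 2-4** (Protocol Table 6-2, footnote 6): "Each PK and IG sample should be collected pre-dose for Week 52 to Week 208".

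The footnote to Table 14-1 states that the samples at Weeks 13 to 16 "refer to the last previous dose given at Week 12 (Dose Reference ID = 3").

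For the weight-and-dose subgroup in the final analysis, the 2023 footnote to SAP Table 2-1 uses a lag: "starting from the next efficacy assessment after the dose change, the subject will be accounted in the new dose group".

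**The concern.** A pre-dose concentration is produced by the injections already given. If a subject enters the new dose group at the visit where the dose changes, that visit's concentration is attributed to a dose the subject has not yet received.

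Take a high-arm subject who weighs 51 kg at Weeks 12 and 16. The dose goes from 150 mg to 300 mg at Week 16, after the blood draw. The Week 16 sample is a 150 mg trough, but on the plain reading of 2.9 it enters the 300 mg, ≥50 kg cell.

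Concentration by actual dose and weight is the table that shows whether the weight-band doses deliver comparable exposure, which Protocol 3.6 gives as the reason for those bands. Subjects aged 6 to under 18 are treated for 208 weeks, so upward moves are likely to be the usual direction. The error would then mostly lower the higher-dose cells rather than average out. Section 2.9 itself accepts that a concentration depends on earlier dosing, because it excludes concentrations at the visit or visits after a missed dose.

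**Working it through.** **1. Sample times.** Hours after the reference dose = (visit week − reference dose week) × 168. For Week 16: (16 − 12) × 168 = 672 h, as printed in Table 14-1. The other printed times also reproduce: 168, 336 and 504 h for Weeks 13 to 15, (208 − 204) × 168 = 672 h, and (224 − 204) × 168 = 3360 h. The protocol therefore ties the Week 16 sample to the Week 12 dose.

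**2. Size of a dose change.** From Protocol Table 5-1, for a one-step upward move:

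| Arm | Weight move | Dose | Ratio |
|---|---|---|---|
| Low | <25 to 25-<50 kg | 75 to 75 mg | 1.0 |
| Low | 25-<50 to ≥50 kg | 75 to 150 mg | 2.0 |
| High | <25 to 25-<50 kg | 75 to 150 mg | 2.0 |
| High | 25-<50 to ≥50 kg | 150 to 300 mg | 2.0 |

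Every one-step upward move that changes the dose doubles it; the reverse halves it. The low-arm move out of the <25 kg band changes only the weight category.

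**3. Visits exposed.** Two consecutive measurements from Week 12 onward are needed, so Week 16 is the first possible change visit. The scheduled site visits with dosing from then on are Weeks 16, 24, 32, 40, 48, 52, 64, 76, 88, 104, 116, 128, 140, 156, 168, 180 and 192: 17 in all. Crossed with Table 14-1, five carry a same-visit PK sample: Weeks 16, 24, 52, 104 and 156. A change at any of the other 12 has no same-visit sample to misfile.

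**4. Effect on a cell.** Assume troughs proportional to dose. If one of the n values in a cell is half the level of the others, the geometric mean is multiplied by 2^(−1/n). After a downward move the factor is 2^(1/n).

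| n in cell | One upward changer | One downward changer |
|---|---|---|
| 5 | 0.871 (−13%) | 1.149 (+15%) |
| 10 | 0.933 (−7%) | 1.072 (+7%) |
| 19 | 0.964 (−4%) | 1.037 (+4%) |

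**5. Plausible n.** About 80 subjects are planned, with at least 5 below 25 kg and at least 10 in each other band. If 5 are below 25 kg, the two upper bands share 80 − 5 = 75 subjects over four dose-by-weight cells: 75 / 4 ≈ 19 each. A band at its floor of 10, split 1:1, gives cells of 5, but both upper bands cannot be at the floor.

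**6. What a lag rule would do.** If the change-visit sample stays with the old dose, the next PK sample follows 2 new-level doses for a change at Week 16 (Weeks 16 and 20), 7 at Week 24, and 13 at each of Weeks 52, 104 and 156. The shortest lead-in at any change visit is one dose (change at Week 48, sample at Week 52).

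**The case against.** The strongest reply is that the SAP does not actually direct the misfiling. Its phrase about concerned assessment points is undefined and could mean only the PK assessments that follow the new dose. The 2023 Table 2-1 footnote also opens by placing subjects in their actual dose and weight groups in the final analysis, and Table 2-2 marks PK concentrations for that subgroup.

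Part of this stands. A reader might infer that the SAP certainly files old-dose troughs under the new dose; the documents do not settle that. But the sentence comes directly after the list of visits at which the change is assessed, in a by-visit table, and nothing excludes the change visit. The footnote's lag is worded for efficacy assessments only, so it does not clearly govern 2.9. Two programmers could build different tables from the same text.

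A reader might also infer that 10-20% of a cell would be misfiled, taking 10 subjects per weight band as the expected size. That figure is a recruitment floor. Because the tables are by visit, 20% of a 10-subject cell would need two subjects changing dose at the same PK visit, and the documents give no count of changes.

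The objection on importance also largely stands. These are descriptive tables with no test or decision rule attached.

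**Conclusion.** The point holds as a defect in the assignment rule of SAP 2.9. On its plain reading the rule puts a concentration in the wrong dose cell by a factor of two; on the looser reading the rule is simply unstated. Either way it needs correcting.

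The size is modest and conditional: about 4% of a cell's geometric mean per upward changer at an average upper-weight cell, and up to about 13% in a cell of 5. This rests on dose-proportional troughs and on the cell sizes worked out above. The documents give no half-life, so carry-over after the first injection of the new dose cannot be quantified.

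It would be wrong to conclude that the trial's exposure or efficacy results are generally compromised. Concentrations by randomized arm do not depend on this regrouping. AUC84-112d, Cmax and Tmax are summarised by arm, and the samples at Weeks 13 to 16 all follow the Week 12 dose. By-dose values up to Week 15 precede any possible change. The co-primary and key secondary analyses are at Week 12.

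**What to change.** Replace the sentence in SAP 2.9 with:

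> For the PK summaries by dose and weight, each concentration is assigned to the dose actually administered at the last injection before the sample, together with the weight category on which that dose was based. A pre-dose sample at the visit where the dose changes stays in the previous dose and weight group; the new group applies from the first sample after an injection of the new dose.

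The weight category has to travel with the dose. A rule that corrected the dose alone would put the 51 kg example in the 150 mg, ≥50 kg cell, which belongs to the low arm. A low-arm subject moving from 75 to 150 mg would land in a 75 mg, ≥50 kg cell that is not among the five groups of Table 2-1. The reference in 2.9 to weight category at the visit needs the same qualification, and the Table 2-1 footnote should be extended so that both sections state one rule.

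To show how settled each subject is on a new dose, list the number of new-level doses received before each sample rather than setting an arbitrary threshold.

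The cost is a short text change and a programming rule using dose records already in the Dosage Administration Record eCRF. Interim tables built under the same sentence should be checked. This concerns analysis grouping only, not dosing.
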